# **11.3.** Performance of the Upper Limb

The Performance of the Upper Limb (PUL) was designed specifically for assessing upper limb function in ambulant and non-ambulant DMD patients (Pane et al., 2014). All the tasks included in the PUL were selected to address patient prioritized activities of daily living that are typical regardless of age, including preschool children. The PUL includes an entry item to define the starting functional testing level for a subject. The remaining PUL items are divided into three regional dimensions: high-level (shoulder), mid-level (elbow), and distal-level (wrist and hand). Trial subjects will complete testing of the 1.2 module using the same preferred arm throughout the course of the trial when PUL testing is required.

Elbow contractures will be measured in each arm of a subject prior to the start of PUL testing at each visit that requires testing.

PUL equipment will be standardized across investigative sites and provided by Capricor. Additional details regarding the PUL requirements can be found in the trial's MOP.

# 11.4. Pulmonary Function Testing

Pulmonary function testing (PFT) in this trial will measure slow vital capacity (SVC), forced vital capacity (FVC), forced expiratory volume in one second (FEV1), peak expiratory flow (PEF), maximum inspiratory pressure (MIP), maximum expiratory pressure (MEP), peak cough flow (PCF), and inspiratory flow reserve (IFR). PFTs will be performed using equipment that meets or exceeds the minimal performance recommendations of the American Thoracic Society/European Respiratory Society and that will be provided by a centralized core lab.

Site personnel must complete a certification exam prior to conducting PFTs with a trial subject.

Subjects will complete PFTs in the seated position prior to any other functional outcome measurements (i.e., PUL 1.2, 6MWT, and cardiac MRI). Every effort should be made to complete a subject's PFTs at approximately the same time in the morning at each trial visit. Additional details regarding each PFT technique and requirements are included in the study reference manual provided by the centralized core lab. This manual should be followed for all pulmonary function testing.

#### 11.4.1. Slow Vital Capacity

SVC maneuvers will be performed prior to spirometry (forced maneuvers) because of the potential for muscular fatigue and volume history effects.

Subjects will perform at least three acceptable SVC maneuvers (with no more than five total attempts) until the highest SVC is no more than 0.150 L greater than the next highest measurement. The largest acceptable SVC value will be reported.

#### 11.4.2. Spirometry

At least three acceptable spirometry efforts (with no more than five attempts) will be obtained for  $FEV_1$ , FVC, and PEF determinations. Acceptable forced maneuvers will have a satisfactory start of test and end of test (i.e., a plateau in the volume-time curve) and be free from artifacts due to cough, early termination, poor effort, obstructed mouthpiece, equipment malfunction, or other reasons.

Quality control standards will be implemented within a testing session. The largest FEV1, FVC, and PEF from the 3 acceptable efforts will be reported, even if they do not come from the same effort. The two largest accepted FVC values should be within  $\pm$  15% of each other. Additionally, the two largest accepted PEF values should be within  $\pm$  15% of each other.

# 11.4.3. Maximal Inspiratory & Expiratory Pressures

Maximal inspiratory pressure (MIP) and maximal expiratory mouth pressure (MEP) are simple tests in which patients generate as much inspiratory or expiratory pressure as possible against a blocked mouthpiece. Because lung volume cannot change significantly during measurement, results are to a large extent independent of the properties of the lungs. They are general tests of neuromuscular function of the combined diaphragm, abdominal, intercostal, and accessory muscles (Evans and Whitelaw, 2009).

Subjects will perform the MIP maneuvers (from residual volume (RV)) first, and the MEP maneuvers (from total lung capacity (TLC)) second.

There must be at least 3 acceptable maneuvers from a maximum of five per session.

The two largest accepted values should be within  $\pm 15\%$  of each other.

Subjects will sustain maximal efforts for a total of 3-4 seconds until a plateau in pressure is achieved for at least 1.5 seconds.

Site personnel must carefully judge outlier efforts, which need to be eliminated if the pressure reading showed no gradual increase to the plateau value, suggesting a sharp peak value.

#### 11.4.4. Peak Cough Flow

Subjects will perform at least three cough maneuvers (with no more than five total attempts) from TLC for PCF determination. Site personnel must evaluate each maneuver to determine if it meets acceptability criteria. The largest, acceptable PCF value will be reported.

#### 11.4.5. Inspiratory Flow Reserve

Subjects will perform at least three maximum inspiratory flow-volume maneuvers (with no more than five total attempts). From stable tidal breathing, subjects will expire to RV and then inspire to TLC with maximum effort. Site personnel must evaluate each maneuver to determine if it meets acceptability criteria. The largest, acceptable inspiratory flow reserve value will be reported.

# 11.5. 6-Minute Walk Test

Subjects assessed by the Investigator as capable of performing the 6MWT will do so on Day 1 and the protocol-specified follow-up visits. Subjects unable to perform the 6MWT on Day 1 will not be required to perform the test at any subsequent visit. Detailed information on performing the 6MWT are found in the trial MOP.

# 11.6. Cardiac MRI

Subjects will undergo cardiac MRI at the Screening and Month 6 visits (or, Early Termination Visit) if they are physically capable as determined by an Investigator. Subjects that complete the cardiac MRI will have sufficient attention span, ability to maintain a breath-hold, lack significant contractures that would otherwise make lying flat difficult and fit properly within the MRI scanner.

A subject's screening cardiac MRI case will require evaluation by a site's radiologist using institutional procedures. The reported LVEF from the local interpretation will be used to assess eligibility (exclusion criterion 1).

It is anticipated that the duration of each MRI session will be 45-60 minutes. Acquisition parameters and techniques are specified in the MRI Imaging Manual. The site-based MRI technologists will be trained and certified in the common acquisition protocol prior to initiation of enrollment at each site. All trial images and applicable imaging data will be sent to and centrally read at an independent, central, imaging core by DMD cardiovascular MRI and imaging experts.

Subjects that cannot complete a cardiac MRI as part of the trial will complete an echocardiogram at screening using the site's local equipment, acquisition protocol, and evaluation procedures.

The reported LVEF from the local interpretation will be used to assess eligibility (exclusion criterion 1).

# **12. OTHER TRIAL ASSESSMENTS**

Other trial assessments will be performed as indicated in Table 3.

### 12.1. Medical Status Questionnaire

Subjects will be evaluated for the following at Day 1 and throughout the course of the trial:

- Frequency of manual/power wheelchair use
- Age permanently transitioned to a wheelchair full time
- Ventilatory support
- Frequency of falls

# **12.2.** Medical History

Relevant and significant medical/surgical history will be confirmed at screening.

# 12.3. Prior and Concomitant Medications

All medications taken within one month prior to the screening visit through trial completion will be captured. Medications will be reviewed at each trial visit and any medication changes, including new and discontinuations, will be recorded.

For each medication, generic name, indication, dose, frequency, route, and starting and stopping dates/times (if applicable) will be collected. The trade name of the medication is to be reported for combination therapies (e.g., Alka-Seltzer, Advair, etc.).

All efforts should be made to maintain the same DMD medication regimen throughout the course of the trial. This should be discussed with the subject's primary medical doctor and caregivers at the outset of the trial and during the trial follow-up period.

# 12.4. Planned Medical/Surgical Procedures

Data associated with any elective medical and/or surgical procedure (e.g., wisdom tooth extraction) that is not the result of an adverse event will also be captured.

For each procedure, the type of procedure, indication, and start date/time will be recorded. Any administered medication(s) related to the planned medical/surgical procedure(s) will be captured as a concomitant medication.

# **13.** ASSESSMENT OF SAFETY

### **13.1.** Safety Parameters

Safety assessments will be performed as indicated in Table 3.

#### 13.1.1. Vital Signs

Heart rate, systolic and diastolic blood pressure, respiratory rate, body temperature, and blood oxygen saturation (SpO2) will be measured after the subject has rested for approximately 5 minutes and before performing ECG and spirometry testing. A single set of values will be captured.

A subject's SpO2 will be monitored for at least 30 minutes following each CAP-1002 infusion (see Section 10.7).

Vital signs will be performed using equipment provided by investigative sites that has been properly calibrated per institutional guidelines.

#### 13.1.2. Weight and Height

Weight and height measurements will be performed.

Investigative sites will make every effort to perform a weight measurement without the subject's wheelchair or other assistive device (e.g., walker), if applicable.

If standing height cannot be measured, height will be calculated using a measurement of ulna length (Gauld et al., 2004). It is critical to reduce variability in ulna length measurements across investigative sites. Therefore, site personnel must complete trial-specific training prior to measuring a subject's ulna length for the purposes of calculating height.

#### Table 5:Height Calculation from Ulna Length

Height (cm) = [4.605 x Ulna Length (cm)] + [1.308 x Age (years)] + 28.003

Centimeter and year entries must include decimal places. If a subject is 18 years or older, enter "18" in the formula for age.

# 13.1.3. Physical Examination

The physical exam (PE) is not considered a standard of care assessment as the examiner will be assessing for research events. Therefore, the physical exam is to be conducted only by an Investigator, or designated site personnel (e.g., nurse practitioners, physician assistants, research fellows) listed on the Delegation of Authority Log.

The physical examination will be a review of the major organ systems including: general appearance, HEENT, lymphatic, respiratory, cardiovascular, chest, abdomen, gastrointestinal, and musculoskeletal.

Clinically significant findings prior to investigational product administration are to be captured as medical history.

Clinically significant findings after the start of investigational product administration are captured and reported as AEs, if they meet the definition of an AE per Section 13.2.1.

# **13.1.4.** Electrocardiogram (ECG)

All ECG measurements will be obtained in the supine position with standardized equipment that meet institutional standards for clinical use. Site personnel must complete trial-specific training prior to ECG measurements. A 12-lead ECG measurement and rhythm strip (10 seconds) will be obtained after measurement of vital signs and before spirometry testing.

The Investigator, a designated Sub-Investigator, or other appropriately trained site personnel will be responsible for performing 12-lead ECG assessments. The Investigator must provide his/her dated signature on the original paper tracing, attesting to the authenticity of the ECG machine interpretation, or their over-read and reinterpretation.

ECG data will be electronically transmitted to an independent cardiologist, contracted by Capricor, and evaluated. The independent cardiologist, blinded to treatment assignment, will conduct an over-read of the ECG measurements required for the trial. Investigative sites will receive a report with the independent cardiologist's ECG interpretations that must be reviewed, signed, and dated by an Investigator.

#### 13.1.5. Immunologic Assessments

Serum for DSA testing and whole blood for HLA typing will be collected following the standard institutional procedures for blood collection and submitted to a central laboratory for analysis. Instructions on collection, processing, storage and shipping the samples to the central laboratory are located in the Laboratory Manual.

DSA collection for the Week 4 and Month 4 ( $\pm$ 7 days, respectively) visits will occur either at the investigative site or remotely at a designated central laboratory patient service center.

DSA samples may also be collected in the setting of clinical suspicion of immune sensitization syndrome in the judgment of the Investigator. See Section 7.2.1 for additional details regarding immune sensitization syndrome as a safety endpoint.

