#### **Objectives**:

*Primary*: To provide CAP-1002 to subjects who were randomized to the Usual Care Treatment Group of the HOPE-Duchenne trial and completed 12 months of follow-up.

*Secondary*: To explore the safety and efficacy of intravenous administration of CAP-1002 with repeat dose at Month 3.

**Methodology:** This Phase 2, multi-center, open label extension trial will provide CAP-1002 to subjects that were randomized to the Usual Care Treatment Group of the HOPE-Duchenne trial (CAP-1002-DMD-01) and explore the safety of two intravenous administrations of CAP-1002, each separated by three months. Subjects will undergo targeted tests and procedures during a 30-day screening period to determine eligibility based on protocol inclusion and exclusion criteria.

Eligible subjects will undergo baseline safety and efficacy assessments on Day 1 prior to their first infusion of CAP-1002. Administration of CAP-1002 (Day 1) should occur within a maximum of 14 days following confirmation of eligibility; if a delay of more than 14 days between enrollment and IP administration is unavoidable, a conversation between the Investigator and Medical Monitor should occur to determine the need for repeat assessments prior to infusion.

All CAP-1002 infusions will be conducted in an outpatient setting at the investigative site on Day 1 and Month 3. Subjects will be observed in the outpatient setting for at least two hours post infusion and then discharged the same day if medically cleared by the site Investigator.

A safety phone call will be performed 14 days ( $\pm 3$  days) after each CAP-1002 infusion, and if clinically indicated, an unscheduled in-person visit will be performed at the investigative site with targeted assessments based on presentation of signs and symptoms.

Blood samples will be collected before each CAP-1002 administration (Day 1 and Month 3), after each CAP-1002 infusion (Week 4 and Month 4) and at Month 6, unless otherwise indicated, for donor specific antibody (DSA) testing and routine serum chemistries, hematology and cardiac enzymes. HLA

typing will occur before the first CAP-1002 administration on Day 1. Collection will occur either at the investigative site or remotely at a designated central laboratory patient service center.

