Trial visits at the investigative site will occur at Months 3 and 6 ( $\pm$ 14 days, respectively). Subjects will complete safety and efficacy assessments prior to CAP-1002 administration at the Month 3 trial visit.

The *primary safety endpoints* include the incidence of the following from baseline through the 6-month timepoint:

- Acute respiratory decompensation within 2 hours following IP administration
- Hypersensitivity reaction
  - Hypersensitivity reaction is defined as a clinical syndrome including, but not limited to, fever, leukocytosis, or rash with onset  $\leq 2$  hours post infusion and lasting < 24 hours, in the absence of clinical signs of concomitant infection.
- All-cause mortality
- Serious adverse events
- Treatment-emergent adverse events related to IP or administration procedure
- Immune sensitization syndrome
  - Immune sensitization syndrome shall be defined as: (a) clinical signs and symptoms consistent with systemic inflammation (e.g., fever, leukocytosis, rash, or arthralgia) with onset ≥ 24 hours post infusion and the absence of clinical signs of concomitant infection, AND (b) elevation of anti-human leukocyte antigen (HLA) antibodies against the donor cells (i.e., DSAs), detected ≤ 30 days following onset of syndrome, of (i) ≥ 2000 mean fluorescent intensity (MFI) if baseline MFI ≤ 1000, or (ii) ≥ 2 times baseline otherwise

The *exploratory endpoints* include the change from baseline to each assessment timepoint for the following assessments:

- All subjects
  - Mid-level (elbow) dimension of the Performance of Upper Limb (PUL) 1.2
  - Mid- and distal-level (elbow) dimension of the PUL 1.2
  - High-level (shoulder) dimension of the PUL 1.2
  - Left ventricular structure and function as assessed by cardiac MRI including regional systolic left ventricular wall thickening ejection fraction, end-diastolic volume, endsystolic volume, stroke volume, regional wall thickness, and circumferential strain
  - Slow vital capacity (SVC), forced expiratory volume in one second (FEV1), forced vital capacity (FVC), peak expiratory flow (PEF), maximum inspiratory pressure (MIP), maximum expiratory pressure (MEP), peak cough flow (PCF), and inspiratory flow reserve (IFR)
- Ambulatory subjects only

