#### 14.4.4. Donor-Specific Antibodies

Donor-specific antibodies (DSA) will be assessed as screening and periodically during the follow-up period or upon clinical suspicion of an immune sensitization response, and will be summarized by the specific CDC donors contributing to the CAP-1002 doses used by individual subjects.

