#### 14.6.2. Missing Data

There are no plans for imputation of missing data. The reasons for missing data will be documented. Sensitivity analyses, however, may be performed using various assumptions for missing data to assess the impact on summary results.

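### Immune sensitization syndrome needs a DSA rise within 30 days of onset, but scheduled draws leave gaps and the event-triggered draw is optional

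*Protocol*

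**What the plan says.** The endpoint is defined in the Protocol Synopsis and repeated in Protocol 7.2.1 and SAP 2.2.1. It has two criteria, and both must be met:

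- (a) signs of systemic inflammation "with onset ≥ 24 hours post infusion and the absence of clinical signs of concomitant infection";
- (b) a DSA rise of stated size, "detected ≤ 30 days following onset of syndrome".

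Criterion (a) sets no upper limit on the time of onset, and incidence is counted "from baseline through the 6-month timepoint".

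Protocol Table 3 and SAP Appendix B schedule DSA on Day 1, Week 4 (Day 30 ±7), Month 3 (Day 90 ±14, before Infusion 2), Month 4 (Day 120 ±7) and Month 6 (Day 180 ±14). The Month 4 draw is given as a trial day. It is not counted from Infusion 2, whereas the 14-day safety call is.

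On sampling outside the schedule, Protocol 13.1.5 says: "DSA samples may also be collected in the setting of clinical suspicion of immune sensitization syndrome in the judgment of the Investigator". Protocol 14.4.4, in the statistics chapter, describes DSA as assessed "periodically during the follow-up period or upon clinical suspicion of an immune sensitization response".

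On missing results, Protocol 14.6.2 says "There are no plans for imputation of missing data" and has the reasons documented. SAP 5.8 lists antibody intensity by subject and visit, and takes DSA up in relation to the syndrome only if one has occurred. Neither document has a category for a clinical syndrome that has no DSA result within its 30 days.

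**The concern.** Protocol 5.6.3 names an immune response to repeated doses of an allogeneic product as a safety question for this trial, and this endpoint is the one built to answer it. Because both criteria must be met, a missing antibody result acts like a negative one: criterion (b) is not met and the subject is not counted. SAP 5.8 adds a circularity, since DSA is examined if a syndrome occurs, yet a syndrome cannot be established without the DSA result.

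This runs opposite to the SAP's handling of other incomplete safety data. SAP 4.3 counts a missing seriousness as serious, a missing severity as severe and a missing relatedness as possible. Here the missing item moves the result toward apparent safety. With at most 10 subjects, one uncounted case changes the observed incidence from 1/10 = 10% to 0/10 = 0%.

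**Working it through.** The plan states no coverage figure, so there is none to reproduce. The check counts the onset days that have a scheduled draw in time.

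**Inputs.** Detection limit: 30 days after onset (Synopsis, 7.2.1). Earliest qualifying onset: Day 2, being 24 h after the Day 1 infusion. Last onset day: the Month 6 draw. Draw days and windows: Table 3.

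**Rule.** Onset on day t is covered if a scheduled draw falls on any day from t to t + 30. For consecutive draws on days A and B, the uncovered onset days run from A + 1 to B − 31, so their number is max(0, B − A − 31). Before the Week 4 draw on day A, uncovered days run from 2 to A − 31, so their number is max(0, A − 32).

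**Nominal days (30, 90, 120, 180).**

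- Before Day 30: max(0, 30 − 32) = 0.
- 30 to 90: 90 − 30 − 31 = 29 (Days 31-59).
- 90 to 120: max(0, 120 − 90 − 31) = 0.
- 120 to 180: 180 − 120 − 31 = 29 (Days 121-149).
- Total 58 of 179 onset days (Days 2-180): 58/179 = 32.4%.

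Reading Week 4 literally as Day 28 gives 31 + 29 = 60, and 60/179 = 33.5%.

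**Permitted windows.** All combinations of the four draw days within their windows were enumerated.

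| Case | Draw days | Uncovered | Share |
|---|---|---|---|
| Most favourable | 32, 76, 113, 166 | 13 + 6 + 22 = 41 of 165 | 24.8% |
| Nominal | 30, 90, 120, 180 | 29 + 0 + 29 = 58 of 179 | 32.4% |
| Least favourable | 23, 104, 113, 194 | 50 + 0 + 50 = 100 of 193 | 51.8% |

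The unweighted mean over all combinations is 34.8%.

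**Where the gaps fall relative to infusion.** On nominal days, onsets up to 28 days after either infusion (Days 2-29 and 91-118, 56 days) are all covered. The gaps lie roughly 30 to 59 days after each infusion. Visits that are in window can change this:

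- Week 4 drawn on Day 37: 37 − 32 = 5 uncovered days, Days 2-6, which lie 35 to 31 days before the draw.
- Infusion 2 on Day 76 and Month 4 on Day 120: 120 − 76 − 31 = 13 uncovered days, Days 77-89.
- Infusion 2 on Day 76 and Month 4 on Day 127: 127 − 76 − 31 = 20 uncovered days, Days 77-96, that is, days 1 to 20 after the second exposure.
- Week 4 on Day 23 and Month 4 on Day 113, with Infusion 2 on Day 90: Days 24-29 and 114-118, 11 of the 56 days.

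None of these is a visit-window deviation.

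**When a late onset would come to light.** Table 3 marks no adverse-event review at Week 4 or Month 4. After each 14-day call, the next marked review is Month 3 or Month 6. A self-limited syndrome starting on Days 31-59 could therefore first be recorded near Day 90, when its 30 days have passed.

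**The case against.** Four points deserve weight.

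First, a reader might infer from 32% that a third of cases would be lost. The documents do not support that. They give no distribution of onset times, and equal weighting of every day to Month 6 is only a way of counting. If onsets cluster in the first four weeks after an infusion, the nominal loss is near zero. What stands is that the permitted windows can open gaps in exactly that period.

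Second, the counts assume that no triggered sample is taken. The protocol provides for one, and also has a call 14 days after each infusion and an unscheduled visit if clinically indicated. Recognising a syndrome is what would prompt the sample. This is fair, but the draw remains at the Investigator's discretion, no timing is attached, and recognition may come after the 30 days.

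Third, a reader might infer that such an event would vanish. It need not. Reported adverse events are listed (SAP 7.1), DSA values are listed by subject and visit (SAP 5.8), and a Clinical Events Committee adjudicates all potential primary safety endpoints. Serious events and related treatment-emergent events are primary safety endpoints in their own right. With 10 subjects, someone who goes looking could find the case. What is lost is its place in this endpoint's count, and the summary table would not show why. The committee cannot supply a sample that was never drawn.

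Fourth, a reader might take 14.4.4 to make the triggered draw mandatory, so that 13.1.5 contradicts it. Its wording joins periodic assessment and clinical suspicion with *or* and sets neither timing nor a duty on sites. The two passages are unaligned and need reconciling, but 14.4.4 does not by itself settle the matter.

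The trial is also an uncontrolled extension with no formal hypotheses. That limits the consequences but does not remove the ambiguity of a zero count.

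**Conclusion.** The concern holds in a bounded form. Followed exactly, the plan can leave a clinical syndrome out of a primary safety endpoint because no sample was required in time. Scheduled draws miss 58 of 179 onset days (32%) on nominal days and 25% to 52% over the permitted windows. The 52% end needs the visits at opposed window limits and should not be quoted alone.

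The figures rest on these assumptions: the draw date is the detection date; a draw on the day of onset counts; a result from before onset does not count as detection after it; the Month 3 draw is taken on the day of Infusion 2; and no triggered draw is made. They measure gaps in the calendar, not the probability of missing a case.

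The absence of a rule for the unresolved case is established only for the protocol and SAP. The CEC Charter, Manual of Procedures and Laboratory Manual were not available and may address it.

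**What to change.** In Protocol 13.1.5, make the DSA draw required whenever immune sensitization syndrome is suspected, to be taken within 30 days of onset, and reconcile 14.4.4 so that both sections state the same obligation. If the syndrome is suspected in time and the draw is made, this takes the uncovered days on the nominal schedule from 58 of 179 to 0 of 179.

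That does not help when a syndrome first comes to light after its 30 days. So in SAP 2.2.1 and Section 7, add a line to the primary safety summary: *clinical criterion (a) met, DSA not evaluable within 30 days*. Report it separately from both confirmed events and non-events. State that any later DSA result is listed with its date but neither confirms nor rules out the endpoint; Protocol 13.2.1.3 describes DSA as possibly transient, so a late negative would not be informative.

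The cost is an occasional extra blood draw, using kits and a central laboratory already in place, and one extra table line.
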